### Study Period 1: Randomized controlled trial:

- 8 subjects randomized to PRP
- 5 subjects randomized to control.
- 

Patients will be randomized to standard treatment procedures versus standard treatment plus intrauterine infusion of platelet rich plasma (PRP). Both groups of patients will receive the same initial workup, consultation and evaluation, treatment, surgical interventions or cycle monitoring, ultrasounds and embryo transfer. The only difference between the two groups will be the intrauterine infusion of PRP based on randomization and that the experimental group will have an extra blood draw for PRP preparation.

The only difference in clinical practice that the experimental group in this randomized controlled trial would have that differed from the "control" population, would be the 1-2 intrauterine infusion of PRP based on randomization and that the experimental group will have an extra blood draw for PRP preparation. The standard of care procedures for patients with Asherman's Syndrome is as following.

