All patients will undergo the hysteroscopic procedure in the operating room under general anesthesia for resection of intrauterine adhesions. The degree of the adhesions will be rated by the physician performing the surgery using ASRM classification guidelines. The scar and adhesions will be resected with hysteroscopic scissors and grasper, until the endometrium appears to be reached with visualization of vascularity. Thereafter, a pediatric 8-10-gauge Foley catheter will be placed into the uterine cavity, and the balloon will be inflated with 3 ml of normal saline. The catheter extending out of the uterus will be tied off with 2 ties of 2'0' silk and then the catheter will be cut distally to the knots, with no parts extending outside of the vagina. Patients will be discharged home the same day and instructed to start on 30 days of 2 mg estradiol twice daily per usual protocol, with 10 days of medroxyprogesterone acetate 10mg daily for the last 10 days of estradiol. All patients will receive doxycycline antibiotic 100mg twice a day for the duration of the intrauterine Foley catheter placement (5-7 days). They will have endometrial lining assessment with transvaginal ultrasound 2 and 4 weeks during the first month post-procedure. Second look hysteroscopy will be performed after 1 month to assess the uterine cavity. Patients will be asked to record the menstrual flow diary before treatment and for the next 1-3 months (Menstrual Assessment Chart, from Higham et al, BJOG 1990). Future fertility treatment will be planned on individual bases per patients' preferences. For the patients with thin endometrial lining, the standard of care guidelines for hormone replacement in the setting of frozen IVF cycles will be used as a reference (not a part of experimental protocol) chosen by the primary physician. The primary doctor will manage the entire hormone replacement based on the clinical knowledge, expertise and standard of care practices. Endometrial lining measured by ultrasound is recorded at every visit. Patients will be undergoing standard controlled frozen embryo transfer (FET) cycle and will be started on oral contraceptive pills (OCP, Desogen) to block the endogenous hormone production for 14-28 days, per usual protocol. GnRH agonist (Leuprolide acetate, Lupron) will be started for pituitary suppression 6-7 days before the last OCP dose, subcutaneously at a dose of 10 units (0.5mg) daily, which will continue until start of progesterone. Patients will present for baseline ultrasound per standard

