7.11 INSTRUMENTS: List all questionn

Study period 2 (10/2/2018):

Prospective recruitment of patients opting for PRP (no randomization; all received intervention.).

- 14 Subjects received PRP using the above protocol

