Platelet-rich Plasma (PRP) for Endometrial Regeneration and Repair NCT02825849

Document Date: Nov 15, 2020

Summary of PRP Study Protocol

Statistical Analysis Plan:

This study was a small, first-in-human pilot study of the use of Platelet Rich Plasma in women with either Asherman's syndrome or think uterine lining. Our over-arching goal was to establish the feasibility of administering and study the impact of PRP in a fertility clinic setting. The primary outcome of this study was improvements in uterine lining. Our secondary outcome was pregnancy rate. We ultimately enrolled 17 subjects into the intervention arm and 5 subjects into the control arm. This study was not powered to detect statistically significant differences. Accordingly, we have calculated and presented descriptive statistics of our baseline characteristics and study outomes. In particular, we have calculated means and standard deviation for continuous outcomes and percentages for dichotomous outcomes.

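### The SAP describes single arms of 17 and 5 with no split by study period, although only 8 v 5 were randomised, so on its natural reading the randomised comparison is not shown

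*SAP*

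**What the plan says.** The SAP is one paragraph. On numbers it says "We ultimately enrolled 17 subjects into the intervention arm and 5 subjects into the control arm". On outcomes it says "The primary outcome of this study was improvements in uterine lining", with pregnancy rate as secondary. It states that the study was not powered for significance and gives that as the reason for descriptive reporting: "we have calculated means and standard deviation for continuous outcomes and percentages for dichotomous outcomes". It names no study period, analysis set, between-arm difference or interval, and does not mention randomisation.

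The Protocol describes two parts. Study Period 1 is a randomised controlled trial: "8 subjects randomized to PRP" and "5 subjects randomized to control". Study period 2 is "Prospective recruitment of patients opting for PRP (no randomization; all received intervention", and there "14 Subjects received PRP using the above protocol".

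On lining measurement, the Period 1 text says of women having adhesions resected: "They will have endometrial lining assessment with transvaginal ultrasound 2 and 4 weeks during the first month post-procedure". In the thin-lining route it schedules a check on cycle day 12 and randomises women whose lining is thin. It also says that lining is recorded at every visit.

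**The concern.** Allocation, not the patient's choice, decided who received PRP only in the 8 v 5 set. An intervention arm of 17 is larger than the 8 randomised to PRP, so it must contain women from elsewhere, and the only other source that the Protocol describes is the self-selected Period 2 group. Period 2 has no controls, and the SAP's 5 controls match Period 1 exactly.

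If the means and percentages are given for these two arms as they stand, any difference between Period 2 and randomised PRP women (in prognosis, motivation, calendar time or mix of diagnoses) passes into the PRP arm's mean or rate. It cannot then be separated from an effect of PRP. A reader can build an interval from a published n, mean and SD, but only for 17 v 5, not for the randomised comparison.

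**Working it through.** **Inputs.** Protocol, Study Period 1: 8 randomised to PRP, 5 to control. Protocol, Study period 2: 14 received PRP, none randomised. SAP: 17 intervention, 5 control. The documents give no SD, effect size or pregnancy rate, so lining precision is in SD units and pregnancy precision is given over all possible results.

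**Reproducing the head counts.**
- PRP: 8 + 14 = 22, against 17 in the SAP. Not reproduced; the gap is 5.
- Control: 5 against 5. Agrees.
- Total: 8 + 5 + 14 = 27, against 17 + 5 = 22. Not reproduced.

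At least two explanations fit the arithmetic, and the documents confirm neither:
- Five of the 14 were former controls, counted only as controls: 8 + (14 − 5) = 17 PRP and 5 control, 22 women.
- Only 3 of the Period 1 PRP women are in the data: 3 + 14 = 17.

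**How many of the 17 were not randomised to PRP.**
- Minimum: 17 − 8 = 9, and 9/17 = 53%. This holds however the gap is explained.
- Maximum: 14, and 14/17 = 82%, if all 17 come from the Protocol's 8 + 14.

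**Effect on a pooled summary.** Let f be the non-randomised share and D the Period 2 value minus the randomised PRP value.

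Pooled = (1 − f) × randomised + f × Period 2 = randomised + f × D

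The PRP mean or rate is shifted by 0.53 D to 0.82 D. The documents do not give D.

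**Precision for lining.** 95% half-width = t(0.975, n1 + n2 − 2) × √(1/n1 + 1/n2), in units of a common SD, with every woman measured.

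| Comparison | t | √(1/n1 + 1/n2) | Half-width |
|---|---|---|---|
| 8 v 5 | 2.201 (11 df) | 0.570 | 1.25 SD |
| 3 v 5 | 2.447 (6 df) | 0.730 | 1.79 SD |
| 17 v 5, pooled | 2.086 (20 df) | 0.509 | 1.06 SD |

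Pooling narrows the nominal interval from 1.25 to 1.06 SD, at the price of the randomised contrast.

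**Precision for pregnancy.** Total width of the Newcombe 95% interval for the difference:
- 8 v 5: 54 to 87 percentage points over all 9 × 6 = 54 possible tables.
- 3 v 5: 71 to 101 points over all 4 × 6 = 24 possible tables.

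As an illustration with assumed counts, 4/8 v 1/5 gives +30 points, 95% CI −21 to +63.

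**Which scan follows randomisation.**
- Thin lining: the day 12 check comes before randomisation, so it is a baseline. No scan is scheduled afterwards, although lining is recorded at every visit.
- Asherman's: scans fall at 2 and 4 weeks after the procedure. The documents do not place randomisation or infusion in time relative to them.

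**The case against.** The strongest reply is that this is a small, openly unpowered pilot, for which descriptive statistics are reasonable. That stands: no test is called for. But lack of power bears on testing, not on whether randomised and self-selected women are shown together. A split by period is itself descriptive.

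Second, the SAP never says that it pools. It gives 17 and 5 as enrolment counts and defines no analysis set. That also stands. A reader might infer that the SAP lays down a pooled 17 v 5 comparison, or that pooling is why no difference is planned. The text supports neither: pooling is the natural reading of a single arm of 17, and the stated reason for descriptive reporting is lack of power. Nor do the documents suggest that the investigators lost the period or arm labels. What would be hidden from a reader of pooled summaries is still available to them.

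Third, n, mean and SD by arm within Period 1 would let a reader derive the lining interval, and the pregnancy count the other. That is fair, and it makes the split the essential part. Stating the difference and its interval costs little more and shows how little 13 women can settle.

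Fourth, a single lining contrast across two routes with different scans and timing may not be meaningful, and a comparable scan after randomisation may not exist in both arms. This stands and limits what can be asked for.

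**Conclusion.** The point holds. As written, the SAP does not show the only randomised comparison in the study, and at least 9 of its 17 PRP women (53%) were not randomised to PRP. The upper figure, 14 of 17 (82%), assumes that all 17 come from the Protocol's 8 + 14. That the summaries are pooled is an inference from the single arm and the silence on periods, so confidence is medium.

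Two stronger conclusions are not supported. The documents do not show that the PRP result is biased in any direction or by any amount, because the difference between Period 2 and randomised PRP women is not given. Nor can precision be fixed at the 8 v 5 values: 1.25 SD and 54 to 87 points apply only if all 8 and all 5 are in the data with a usable measurement. They become 1.79 SD and 71 to 101 points if only 3 randomised PRP women are. The lining figures also assume one common SD across both routes.

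**What to change.** 1. Before fixing any denominator, reconcile the SAP's 17 PRP subjects with the Protocol's 8 + 14 = 22. State whether any woman is counted in both periods, for example a former control who later received PRP; otherwise separate reporting could count her twice without saying so.
2. Report Period 1 by randomised arm: n, mean and SD of the lining outcome, and the pregnancy rate. Add the PRP-minus-control difference with a 95% CI (t-based for lining, Newcombe for pregnancy) and no p-value. Label it post hoc, since the SAP describes calculations already done.
3. Describe Period 2 separately as uncontrolled. Do not present a 17 v 5 contrast, or a change within one arm, as an effect of PRP.
4. Apply one rule for the lining measurement in both arms: a scan confirmed to follow randomisation, with its baseline, because the outcome is an improvement. Show it by route (Asherman's, thin lining) with counts per arm. In the thin-lining route the day 12 check serves as baseline. Use the 4-week Asherman's scan only if it is confirmed to follow randomisation. If no comparable scan after randomisation exists in both arms, say so and give arm summaries only.

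The cost is a few SAP lines and a little analysis of existing data. Whether a comparable scan exists has to be checked in the records. The intervals will be wide, and the report should say so.

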
practice on second day of menses after OCP withdrawal. If baseline ultrasound normal, patients will start Vivelle estradiol patch 0.1mg every 36 hours with increasing dose, again per standard protocol. Surveillance ultrasound lining check will be scheduled on cycle day 12. Per our standard protocol, minimal endometrial strip thickness of 7mm is required before initiation of progesterone. If patients meet the criteria for embryo transfer, it will be performed according to the standard of care. If the lining is thin, patient will be randomized to control or study group.

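### The primary outcome is summarised without using the lining recorded at entry, so part of any chance baseline difference in the randomised 8 v 5 carries into a comparison of the arm means

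*SAP*

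**What the plan says.** The SAP names the outcome: "The primary outcome of this study was improvements in uterine lining". It does not say whether improvement means change from entry, a final value or a responder proportion, and it gives no visit. Its whole analysis is "we have calculated means and standard deviation for continuous outcomes and percentages for dichotomous outcomes". Baseline characteristics are to be described, but no model, covariate or between-arm estimate is stated. The SAP says the study was not powered for statistically significant differences.

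The protocol (Study Period 1) provides a possible covariate: "Endometrial lining measured by ultrasound is recorded at every visit". For women in a frozen embryo transfer cycle, the lining check leads to allocation: "If the lining is thin, patient will be randomized to control or study group".

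The randomised set is "8 subjects randomized to PRP" and "5 subjects randomized to control". Study period 2 adds women who opted for PRP: "14 Subjects received PRP using the above protocol". The SAP reports on a different grouping: "We ultimately enrolled 17 subjects into the intervention arm and 5 subjects into the control arm".

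**The concern.** The SAP states an aim of studying the impact of PRP and reports by arm, so readers will set the two arm means side by side whether or not a test is planned. In a set this small, the arms can easily start with different linings. If improvement is a change score, the arm that started thinner will tend to show the larger gain with no PRP effect. If it is a follow-up value, the arm that started thicker keeps part of its advantage. An unadjusted mean and SD leaves this mixed with any treatment effect, although the measurement needed to separate them is, at least in part, already recorded. Adding an unadjusted 8 v 5 difference with an interval would not remove it.

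**Working it through.** **Inputs.** Arm sizes 8 and 5 come from the protocol, Study Period 1. The documents give no SD, correlation, effect size or alpha, so the plan has no figure of its own to reproduce. Results are in SD units, and the correlation (rho) is assumed over a range.

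**Size of the chance imbalance.** The standard error of the baseline mean difference d is sqrt(1/8 + 1/5) = sqrt(0.325) = 0.570 SD. Its expected absolute size is 0.570 × sqrt(2/π) = 0.455 SD. The chance that it exceeds 0.5 SD is 2 × P(Z > 0.5/0.570) = 38%. It exceeds one standard error in about 32% of randomisations.

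**How much carries over.** Let b be the slope of follow-up on baseline. With no treatment effect, the expected arm difference given d is:
- follow-up values: b × d;
- change scores: −(1 − b) × d;
- baseline-adjusted: about 0.

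With equal SDs and no selection, b = rho. Simulation (40,000 trials of 8 v 5 at each of rho 0.3, 0.5, 0.7 and 0.9) gave slopes on d within 0.01 of these values. For adjustment they ran from −0.008 to 0.006.

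**Conditional bias, no selection.** Given that d exceeds one standard error, its mean size is 0.570 × φ(1)/(1 − Φ(1)) = 0.570 × 0.2420/0.1587 = 0.869 SD. Multiplying by b or by 1 − b:

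| rho | follow-up values | change scores (opposite sign) |
|---|---|---|
| 0.3 | 0.26 | 0.61 |
| 0.5 | 0.43 | 0.43 |
| 0.7 | 0.61 | 0.26 |

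Simulation gave 0.25, 0.44 and 0.62 for follow-up values and 0.62, 0.43 and 0.26 for change, which agree within simulation error. After adjustment the bias was below 0.01.

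**Effect of selecting thin linings.** Selection on baseline leaves b unchanged but narrows the baseline spread. Suppose only baselines below a cut-off c (in population SDs) are enrolled, and let λ = φ(c)/Φ(c). The remaining variance is 1 − cλ − λ²:
- c = 0: 1 − 0.637 = 0.363, SD 0.603;
- c = −1: 1 + 1.525 − 2.326 = 0.199, SD 0.446.

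The mean imbalance beyond one standard error becomes about 0.603 × 0.869 = 0.524 and 0.446 × 0.869 = 0.388 population SD. Multiplying by 0.3 and 0.7 gives 0.16 to 0.37 at c = 0 and 0.12 to 0.27 at c = −1. Over both cut-offs the range is therefore about 0.12 to 0.37 on either scale. At rho 0.5, simulation gave 0.27, 0.23 and 0.20 for change at cut-offs 0, −0.5 and −1.

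**Precision.** With N = 13 and no selection, the standard error is 0.570 for follow-up values, 0.570 × sqrt(2(1 − rho)) for change, and 0.570 × sqrt((1 − rho²)(1 + 1/9)) for adjustment:

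| rho | follow-up | change | adjusted |
|---|---|---|---|
| 0.3 | 0.570 | 0.675 | 0.573 |
| 0.5 | 0.570 | 0.570 | 0.520 |
| 0.7 | 0.570 | 0.442 | 0.429 |
| 0.9 | 0.570 | 0.255 | 0.262 |

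Adjustment beats follow-up values only when (1 − rho²) × 10/9 < 1, that is, rho above 0.32. It beats change only when (1 + rho) × 10/9 < 2, that is, rho below 0.8. With selection at population rho 0.5, the adjusted standard error is about 0.52 against 0.51 to 0.52 unadjusted, so there is almost no gain.

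**The case against.** The strongest reply is that the SAP estimates no PRP effect. It presents a pilot whose overall goal includes feasibility, says it is unpowered, and limits itself to description for that reason. Its groups are 17 v 5, not 8 v 5. Since only 8 women were randomised to PRP, at least 17 − 8 = 9 of the 17 lie outside that arm. Period 2 women chose PRP, and adjusting for lining would not cure that. All of this stands, and it is why the adjusted estimate belongs to the randomised set alone and should be called exploratory. It does not remove the problem, because arm-wise means invite the comparison.

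A reader might infer four stronger points that the documents do not support:
- **The imbalance passes in full into the apparent effect.** It does so only at the extremes (b = 1 for follow-up values, b = 0 for change). Because improvement is undefined, even the direction is open. A responder definition is also possible, since percentages are planned for dichotomous outcomes. Over all randomisations the unadjusted difference is unbiased; the bias is conditional on the imbalance that occurred.
- **Selecting a low scan makes it worse.** Selection lowers the correlation but not the slope, and it shrinks the baseline spread, so the bias falls.
- **Adjustment buys precision.** At N = 13 it may not, particularly after selection.
- **All 13 women have a usable entry scan.** A lining check before allocation is explicit only for thin-lining women. For women with intrauterine adhesions, the protocol states scans at 2 and 4 weeks after surgery, but neither a scan before allocation nor the time of allocation.

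**Conclusion.** The concern holds in a limited form. The plan leaves an available baseline value out of the summary of its primary outcome, and with 8 v 5 the chance imbalance can be large enough to matter to anyone who compares the arms. The 0.25 to 0.62 SD range rests on equal SDs, no selection and rho from 0.3 to 0.7. The 0.12 to 0.37 population SD range rests on the same rho with assumed cut-offs from 0 to −1 SD. The second is nearer to the thin-lining women, but the documents give no lining SD with which to place a cut-off on that scale. This is a low-cost improvement to a descriptive pilot. It does not invalidate the SAP's summaries, and it says nothing about the larger problem of pooling self-selected Period 2 women. The PRP counts (8 + 14 = 22 against 17 in the SAP) also need reconciling, as a separate matter.

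**What to change.** In the SAP, for the Period 1 randomised set only:

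1. Define the follow-up visit at which lining is assessed and the scale on which improvement is reported.
2. Regress follow-up lining on arm and the last lining recorded before allocation. Report the PRP-minus-control difference with a 95% t interval, labelled exploratory. Degrees of freedom are 10 if all 13 women have both scans, otherwise N − 3. State how many entry scans are missing and, for the women with adhesions, which scan counts as entry.
3. Show entry and follow-up means and SDs by randomised arm beside it.
4. Keep Period 2 women out of this estimate.

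The cost is a few lines of text, one regression and one residual degree of freedom (t critical value 2.228 instead of 2.201). If entry and follow-up lining were uncorrelated, the mean 95% half-width would be about 1.30 SD against 1.22 for raw follow-up means (1.30/1.22 = 1.07, so 6 to 7% wider). No new data are needed where the entry scan exists.
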